 Thorough physical/medical examination includes, but is not limited to B-symptoms, cardiovascular, gastrointestinal, hepatobiliary, respiratory, skin, musculoskeletal, genitourinary/renal and other organ systems.

 A targeted physical examination to focus on areas involved by AEs or areas involved by WM (e.g. splenomegaly, lymphadenopathy) and for B-symptoms

 Vital signs include heart rate, blood pressure and temperature. Vital signs will be done on day 1, day 8 and day 15 during the first 6 cycles for the first 10 patients. For all other patients only on day 1 and day 15 vital signs measurement is necessary.

A 12-lead ECG (including PR-, QT- and QTc interval) will be performed at every mentioned time point

a) On day 1, cycle 1 optional in the discretion of the investigator (depending on local standards and the timeframe between screening ECG and day 1)

b) The first 10 patients in the study in arm A will be monitored more closely during the first 6 cycles. ECG will be done on day 1 and day 15 during the first 6 cycles for the first 10 patients.

-  Transthoracic echocardiography will be performed at screening and after that every 6 months (screening, cycle 7, cycle 13, cycle 19, cycle 25 etc.) or if clinically indicated.
-  A pulmonary function test will be performed at screening and thereafter only if clinically indicated.
-  If hyperviscosity syndrome is suspected a fundoscopy has to be performed.
-  The laboratory values will be performed only locally, a detailed laboratory flow chart can be found in the appendix of the protocol.
-  Pregnancy test must be repeated after two weeks during screening, after that monthly pregnancy test are mandatory (pregnancy test strips will be supplied by the sponsor for the 3-monthly treatment phase)
-  CBC with diff will be done on day 1, day 8 and day 15 during the first 6 cycles for the first 10 patients. For all other patients only on day 1 and day 15 CBC with diff is necessary. Screening values can be used for Cycle 1, day 1 in the discretion of the investigator (depending on local standards and the timeframe between screening laboratory and day 1).

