-  Serum chemistry (sodium, potassium, calcium, creatinine, total bilirubin, SGOT, SGPT, LDH, magnesium, phosphate, glucose, urea or BUN, CRP, total protein, albumin) will be done on day 1, day 8 and day 15 during the first 6 cycles for the first 10 patients. For all other patients only on day 1 and day 15 during cycle 1 to 12 serum chemistry is necessary. Screening values can be used for Cycle 1, day 1 in the discretion of the investigator (depending on local standards and e.g. the timeframe between screening laboratory and day 1). Serum electrophoresis will be done only every 6 months.
-  B2-microglobulin will be done every 6 months (screening, cycle 7, cycle 13, cycle 19, cycle 25 etc.).
-  INR and partial thromboplastin time (activated or not). Screening values can be used for Cycle 1, day 1 in the discretion of the investigator (depending on local standards and e.g. the timeframe between screening laboratory and day 1).
-  Urine analysis will be performed from cycle 13 every 6 months (screening, cycle 7, cycle 13, cycle 19, cycle 25 etc.) until end of treatment.
-  If cryoglobulinemia is suspected cold agglutinin test and direct Coombs test will be done at screening and after that every 6 months (screening, cycle 7, cycle 13, cycle 19, cycle 25 etc.) if initially positive.
-  Testing for HbsAg and anti-Hbc is obligatory for the Hepatitis B serology. In case the patient is positive for either HbsAg and/or anti-Hbc, patients can be only included if HBV-DNA is negative. In this case Hepatitis B prophylaxis has to be initiated and HB-DNA in these patients needs to be re-evaluated in regular intervals according to local guidelines. HBV-DNA positive patients may not be included into the study.
-  All tumor lesions at screening will be followed as target or non-target lesions. For screening evaluation a routine CT (or MRI) within 3 months prior to informed consent can be used for this study. Further assessments during treatment if clinically indicated or in case of initial lymph node / splenomegaly.
-  Bone marrow aspirate and biopsy will be performed from cycle 13 every 6 months (cycle 19, cycle 25 etc.) until end of treatment (only if CR or delayed response is expected).

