 Relevant medical history not pertaining to the study indication started before signing informed consent over the last 5 years and assessments of any current medical conditions. Previous therapies for WM will also be documented.

 Thorough physical/medical examination includes, but is not limited to B-symptoms, cardiovascular, gastrointestinal, hepatobiliary, respiratory, skin, musculoskeletal, genitourinary/renal and other organ systems.

 A targeted physical examination to focus on areas involved by AEs or areas involved by WM (e.g. splenomegaly, lymphadenopathy) and for B-symptoms.

 Vital signs include heart rate, blood pressure and temperature.

 A 12-lead ECG (including PR-, QT- and QTc interval) will be performed at every mentioned time point. On day 1, cycle 1 optional in the discretion of the investigator (depending on local standards and the timeframe between screening ECG and day 1)

 Transthoracic echocardiography will be performed at screening and after that every 6 months (screening, cycle 7, cycle 13, cycle 19, cycle 25 etc.) or if clinically indicated.

 A pulmonary function test will be performed at screening and thereafter only if clinically indicated.

 If hyperviscosity syndrome is suspected a fundoscopy has to be performed.

 The laboratory values will be performed only locally, a detailed laboratory flow chart can be found in the appendix of the protocol.

 Pregnancy test must be repeated after two weeks during screening, after that monthly pregnancy test are mandatory (pregnancy test strips will be supplied by the sponsor for the 3monthly treatment phase)

 Serum chemistry (sodium, potassium, calcium, creatinine, total bilirubin, SGOT, SGPT, LDH, magnesium, phosphate, glucose, urea or BUN, CRP, total protein, albumin) will be done on day 1 of each cycle. Screening values can be used for Cycle 1, day 1 in the discretion of the investigator (depending on local standards and e.g. the timeframe between screening laboratory and day 1). Serum electrophoresis will be done only every 6 months.

 B2-microglobulin will be done every 6 months.

 INR and partial thromboplastin time (activated or not). Screening values can be used for Cycle 1, day 1 in the discretion of the investigator (depending on local standards and e.g. the timeframe between screening laboratory and day 1).

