## 13.4.8 Abnormal Laboratory Values

An abnormal laboratory value is considered to be an AE if the abnormality is clinically significant in the discretion of the investigator at the site (e.g. results in discontinuation from the study; requires treatment, modification / interruption of IMP dose, or any other therapeutic intervention; or is judged to be of significant clinical importance).

Regardless of severity grade, only laboratory abnormalities that fulfill a seriousness criterion need to be documented and reported as a SAE.

If a laboratory abnormality is one component of a diagnosis or syndrome, then only the diagnosis or syndrome should be recorded on the AE page of the eCRF. If the abnormality laboratory value was not a part of a diagnosis or syndrome, then the abnormal laboratory value should be recorded as an AE.

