### HA: RRA > RRB

where RRA is the CR / VGPR rate in arm A (Carfilzomib / Ibrutinib) and RRB is the CR / VGPR rate in arm B (Ibrutinib). If the obtained one-sided p-value is less than or equal to 0.1 and the point estimate for the CR / VGPR rate of arm A is larger than that of arm B, it will be concluded that the Carfilzomib / Ibrutinib combination statistically significantly increases CR / VGPR rate compared to single agent Ibrutinib. Additionally, the two-sided 95% confidence interval (CI) of the rate difference (RRA-RRB) will be calculated as effect estimator. Further exploratory analyses of the primary study endpoint encompass the Cochran-Mantel-Haenszel (CMH) test of rate difference adjusting for stratification factors (MYD88 and CXCR4 status and number of prior lines). A CMH 95% stratified confidence interval (CI) of the rate difference (RRA-RRB) with each rate weighted by the number of patients in each stratification factor combination will be calculated as an effect estimator. Additionally, logistic regression models will be used to investigate the influence of putative risk factors on the CR / VGPR rate.

All secondary endpoints will be analyzed exploratory. Group comparisons in binary endpoints will be performed two-sided using the chi square test or Fisher's exact test as appropriate. Additionally, 95% CIs will be calculated for group differences. Survival times will be analyzed using the Kaplan-Meier estimator incl. 95% CI. Furthermore, the Cox Proportional Hazard model will be used to investigate the influence of putative risk factors on survival time. Group comparison in quality of life (ordinal endpoint) will be performed using the Wilcoxon rank-sum test. Additionally, the 95% CI will be calculated for the difference of the medians.

For safety analysis of the RCT, all adverse events will be listed and the frequencies of the most frequent will be calculated. Group comparisons (A vs. B) of frequencies of AEs and SAEs will be performed using the chi square test or Fishers exact test as appropriate.

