Immunglobuline																				
IgM			х	х			х		х		х		х		х		х		х	х
IgA			х	х			х		х		х		х		Х		х		x°	х
IgG			х	х			х		х		х		х		Х		х		x°	х
Serum free light chain																				
Free kappa			х								х									х
Free lambda			х								х									х
Kappa / lambda ratio			х								Х									х
FACS analysis periphe	ral blood																			
FACS	х										х				х				x°	х

\* only for the first 10 patients in Arm A

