## 21.5 Appendix E: Laboratory Flow Chart Arm B

PERIODS	S	SCREENI	EENING TREATMENT (28 days cycles)															
	L	ıp to 45 da	ays		Arm B: Ibrutinib until disease progression or non-tolerable toxicity (max. 7 years after FPI)													
VISITS		Screenin	ng	Cycle 1 to 6 (every 28 days)	Cycle 7	Cycle 8 to 12 (every 28 days)	Cycle 13	Cycle 14 to 18 (every 3 months)	Cycle 19	Cycle 20 to 24 (every 3 months)	Cycle 25+ (every 3 months)	ЕОТ						
	Day -45 to 0	Day -30 to 0	Day -7 to 0	D1	D1	D1	D1	D1	D1	D1	D1	Visit						
Haematology																		
Leucocytes			х	х	х	х	Х	х	х	х	х	х						
Haemoglobin			Х	х	Х	х	Х	х	х	х	х	Х						
Haematocrit			х	х	х	х	х	х	х	х	х	х						
Platelets			Х	х	Х	х	Х	х	х	х	х	Х						
Erythrocytes			х	х	х	х	Х	х	х	х	х	х						
Lymphocytes			Х	х	Х	х	Х	х	х	х	х	Х						
Monocytes #			х	х	х	х	Х	х	х	х	х	х						
Neutrophils			Х	х	х	х	Х	х	х	Х	Х	х						
Eosinophils#			х	х	х	х	Х	х	х	х	х	х						
Basophils#			Х	х	Х	х	Х	х	х	х	х	Х						
Serum chemistry																		
Sodium#			х	х	х	х	Х	х	х	х	х	х						
Potassium#			х	х	х	х	Х	х	х	х	х	х						
Calcium#			х	х	х	х	Х	х	х	х	х	х						
Phosphate #			х	х	х	х	Х	х	х	х	х	х						
Creatinine			х	х	х	х	Х	х	х	х	х	х						
GFR (CKD-EPI)			х	х	х	х	Х	х	х	х	х	х						
Urea or BUN#			х	х	х	х	Х	х	х	х	Х	х						
Glucose #			х	х	х	х	Х	х	х	х	х	х						
Total bilirubin			х	х	х	х	Х	х	х	х	Х	х						
ASAT			х	Х	х	х	Х	x	x	x	x	х						
ALAT			х	х	х	х	Х	x	x	x	x	х						
LDH			х	х	х	х	х	х	х	x	х	х						
Albumin			х	х	х	х	Х	х	х	x	х	х						
PERIODS	SCREENING up to 45 days Screening			TREATMENT (28 days cycles)       Arm B:     Ibrutinib until disease progression or non-tolerable toxicity (max. 7 years after FPI)														
---	---	--------------------	----------------	--	---------	-------------------------------------	----------	---------------------------------------	----------	---	----------------------------------	-------	--					
VISITS				Cycle 1 to 6 (every 28 days)	Cycle 7	Cycle 8 to 12 (every 28 days)	Cycle 13	Cycle 14 to 18 (every 3 months)	Cycle 19	Cycle 20 to 24 (every 3 months)	Cycle 25+ (every 3 months)	ЕОТ						
	Day -45 to 0	Day -30 to 0	Day -7 to 0	D1	D1	D1	D1	D1	D1	D1	D1	Visit						
Magnesium#			х	х	х	х	Х	х	х	х	х	х						
Total protein			х	x	х	х	Х	х	х	х	х	х						
CRP#			х	x	х	х	Х	х	х	х	х	х						
ß2-microglobulin°			х		х		Х		х		X°							
Serum protein electroph	oresis																	
M-protein			х		х		Х		х		X°							
Serum immunofixation																		

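### Blood counts and chemistry are scheduled 37 to 43 times in arm A and 16 times in arm B over cycles 1–24, so the direct comparison of adverse event frequencies tends to find short-lived, symptomless laboratory events more often in arm A

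*Protocol*

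**What the plan says.** Section 14.3 compares the arms on adverse events with no allowance for how often patients are sampled: "Group comparisons (A vs. B) of frequencies of AEs and SAEs will be performed using the chi square test", or by Fisher's exact test. Section 8.5 summarises events by worst CTCAE grade. Section 13.4.8 links laboratory results to adverse events: "An abnormal laboratory value is considered to be an AE if the abnormality is clinically significant". The investigator judges this, and a need for treatment or a change to study drug is among the examples given.

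The schedules are as follows.

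- **Arm A, counts (Table 1, footnote 18).** "CBC with diff will be done on day 1, day 8 and day 15 during the first 6 cycles for the first 10 patients"; then "For all other patients only on day 1 and day 15 CBC with diff is necessary".
- **Arm A, chemistry (Table 1, footnote 19).** "For all other patients only on day 1 and day 15 during cycle 1 to 12 serum chemistry is necessary".
- **Arm A, Appendix D.** Days 1 and 15 through cycle 13, with a day-8 column in cycles 1–6 marked "only for the first 10 patients in Arm A". Then day 1 of every cycle to 24, then three-monthly.
- **Arm B.** Table 2, footnote 18 says chemistry "will be done on day 1 of each cycle". Appendix E shows day 1 through cycle 13 and three-monthly sampling from cycle 14, which Table 2 places at cycles 16, 19 and 22.
- **ECG (Tables 1 and 2).** Day 1 in both arms to cycle 13, plus extra tracings for the first 10 arm A patients in cycles 1–6. In cycles 14–24, every cycle in arm A and cycles 16, 19 and 22 in arm B.
- **Extra sampling.** Section 12.4.12 moves patients with cytopenia to monthly samples from cycle 25 in arm A and cycle 14 in arm B. It also allows tests when clinically indicated.

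Section 12.2 does not agree with this. It lists day-8 and day-15 laboratory tests in cycles 1–6 as an addition for the first 10 arm A patients, whereas footnotes 18 and 19 and Appendix D give day 15 to all arm A patients.

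**The concern.** A transient fall in platelets or neutrophils, or a brief rise in liver enzymes, is recorded only if someone takes blood while it lasts. The arm with more scheduled samples will record more such episodes, and a worst-grade summary can only rise with more looks. This is separate from unequal time on treatment: with the same follow-up and the same true rates, the recorded frequencies would still differ.

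Section 14.2 argues that the hoped-for gain in deep remissions makes the risk-benefit ratio of adding carfilzomib acceptable. The adverse event comparison supplies the risk side. If part of an excess in laboratory events comes from the calendar, the reader needs to be able to see how much.

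**Working it through.** The protocol gives no figure for sampling intensity, so the visits are counted from Appendices D and E.

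**1. Scheduled count and chemistry visits**

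| Cycles | Arm A, most patients | Arm A, first 10 | Arm B | Ratio, most / first 10 |
|---|---|---|---|---|
| 1–6 | 6×2 = 12 | 6×3 = 18 | 6 | 2.0 / 3.0 |
| 7–12 | 6×2 = 12 | 12 | 6 | 2.0 / 2.0 |
| 13 | 2 | 2 | 1 | 2.0 / 2.0 |
| 14–24 | 11 | 11 | 3 | 3.7 / 3.7 |
| **1–24** | **37** | **43** | **16** | **2.3 / 2.7** |

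From cycle 25 both arms are sampled every three months, a ratio of 1.0.

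**2. How far the count depends on the conflicting passages.** Table 1 shows no day-15 sample in cycle 13. On that reading the totals are 36 (42 for the first 10) against 16. If Section 12.2 is taken literally, arm A patients after the first 10 have 12 against 12 in cycles 1–12 and 24 against 16 in cycles 1–24, a ratio of 1.5. The 11 against 3 in cycles 14–24 is the same on every reading.

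**3. Share of episodes caught by scheduled visits.** For an episode of d days starting at a random time, the share caught is the sum over sampling gaps of min(gap, d), divided by 24×28 = 672 days. By Appendix D most arm A patients have 26 gaps of 14 days and 11 of 28 days. Arm B has 12 gaps of 28 days and 4 of 84 days, the last ending at cycle 25.

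| Episode length | Arm A | Arm B |
|---|---|---|
| 7 days | 37×7/672 = 39% | 16×7/672 = 17% |
| 14 days | 37×14/672 = 77% | 16×14/672 = 33% |
| 28 days | (26×14 + 11×28)/672 = 100% | 16×28/672 = 67% |
| 84 days | 100% | (12×28 + 4×84)/672 = 100% |

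In cycles 1–12 both arms catch every 28-day episode, so the 28-day difference comes entirely from the later cycles. On the literal reading of Section 12.2, arm A has 24 gaps of 28 days and catches 24×7/672 = 25% of 7-day, 50% of 14-day and 100% of 28-day episodes.

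**4. Effect on a between-arm test (illustration).** Assumptions, not protocol figures: equal true rates, 0.5 episodes per patient over 24 cycles, scheduled visits only, and a two-sided 5% chi-square test. Section 14.2 supplies 47 patients per arm. The share of patients with at least one detected event is 1 − exp(−0.5 × share caught).

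| Episode length | Arm A | Arm B | Simulated rejection rate |
|---|---|---|---|
| 7 days | 17.5% | 8.0% | about 30% |
| 14 days | 32.0% | 15.4% | about 47% |
| 28 days | 39.3% | 28.3% | about 20% |
| 84 days | 39.3% | 39.3% | about 5% |

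Over 0.25 to 2 episodes per patient and durations of 5 to 84 days, the rejection rate runs from about 5% to 87%.

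**The case against.** **Not every abnormal value becomes an event.** Section 13.4.8 requires clinical significance, so a mild dip need not count. This reduces the effect but does not remove it. Day 15 is a carfilzomib dosing day, and Table 6 ties platelet and neutrophil counts to holding that drug. Section 13.4.8 gives dose modification as an example of significance. A low day-15 count in arm A can therefore become an event, while arm B has no scheduled sample on that day.

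**The protocol has partial remedies.** Once cytopenia is known, arm B goes to monthly samples from cycle 14, matching arm A's day-1 schedule, and unscheduled tests are allowed. This stands, and the figures above ignore both. The cytopenia must first be found, however.

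**The comparison is exploratory, the bias goes against the experimental arm, and visit-matched summaries are ordinary SAP content.** The first two points are true and lower the weight of the finding. On the third, the protocol itself fixes both the unequal schedules and the unadjusted comparison, so a SAP that follows Section 14.3 inherits the problem.

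**Stronger readings.** A reader might infer that laboratory toxicity must look two to three times higher in arm A by construction. The documents do not support that. The ratio varies from 1.0 to 3.7 by period, long-lasting abnormalities are caught equally, and symptomatic events and most SAEs do not depend on scheduled samples. A reader might also infer a spurious fall in toxicity over time as sampling thins out. The protocol plans no analysis of adverse events by cycle or period, so no planned result would show it.

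**Conclusion.** The concern holds for laboratory and ECG events that are short and without symptoms, during cycles 1–24. Laboratory sampling is 2.3 times as frequent in arm A by Appendices D and E (2.7 for its first 10 patients; 1.5 for the others on the literal reading of Section 12.2). Scheduled visits alone would favour detection in arm A by about 39% to 17% for 7-day episodes and 77% to 33% for 14-day episodes, with no difference at 84 days. Episode length and rate are assumptions, and unscheduled tests would narrow these gaps by an amount the protocol does not allow one to calculate. It does not follow that an observed excess in arm A is an artefact. The plan as written gives no means of separating detection from toxicity for these events. A change is worth making, but neither the primary analysis nor the sample size is affected.

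**What to change.** Keep the full comparison of AEs and SAEs and all listings, and state unequal sampling as a limitation of that comparison. Add to Section 14.3 a supplementary A-versus-B comparison of laboratory abnormalities at time points scheduled in both arms: day 1 of cycles 1–13, 16, 19 and 22, then the visits from cycle 25.

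- Use the values recorded in the eCRF. Platelets, neutrophils, haemoglobin, creatinine, bilirubin and transaminases are available there.
- Analytes marked # in Appendices D and E are not entered in the eCRF, and Section 12.4.9 keeps ECG tracings at the site. For these, assign events to common or arm-A-only visits by AE onset date.
- Report events found only at arm-A-only visits descriptively.
- Reconcile Section 12.2, footnotes 18 and 19 of Table 1, the cycle-13 column of Table 1 and Appendix D on day-15 sampling.

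The cost is a few sentences and one derived flag, with no new data or visits. The downside must be stated: from cycle 2 to cycle 24, day 1 falls 14 days after the last scheduled carfilzomib dose (day 15 to day 29). The common-visit comparison can therefore understate toxicity in arm A. It must be read beside the full comparison and must not replace it.

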	where RRA is the CR/VGPR rate in arm A (Carfilzomib / Ibrutinib) and RRB is the CR / VGPR rate in arm B (Ibrutinib). If the obtained one-sided p-value is less than or equal to 0.10 and the point estimate for the CR / VGPR rate of arm A is larger than that of arm B, it will be concluded that the Carfilzomib / Ibrutinib combination statistically significantly increases CR / VGPR rate compared to single agent Ibrutinib. Additionally, the two-sided 95% confidence interval (CI) of the rate difference (RRA-RRB) will be calculated as effect estimator. Further exploratory analyses of the primary study endpoint encompass the Cochran- Mantel-Haenszel (CMH) test of rate difference adjusting for stratification factors (MYD88 and CXCR4 status and number of prior lines). A CMH 95% stratified CI of the rate difference (RRA-RRB) with each rate weighted by the number of patients in each stratification factor combination will be calculated as an effect estimator. Additionally, logistic regression models will be used to investigate the influence of putative risk factors on the CR / VGPR rate. All secondary endpoints will be analyzed exploratory. Group comparisons in binary endpoints will be performed two-sided using the chi square test or

	Fisher's exact test as appropriate. Additionally, 95% CIs will be calculated for group differences. Survival times will be analyzed using the Kaplan-Meier estimator incl. 95% CI. Furthermore, the Cox Proportional Hazard model will be used to investigate the influence of putative risk factors on survival time. Group comparison in quality of life (ordinal endpoint) will be performed using the Wilcoxon rank-sum test. Additionally, the 95% CI will be calculated for the difference of the medians. For safety analysis of the RCT, all adverse events will be listed and the frequencies of the most frequent will be calculated. Group comparisons (A vs. B) of frequencies of AEs and SAEs will be performed using the chi square test or Fishers exact test as appropriate.
Duration of recruitment	Q2 2024
Duration of the study for individual patient	Until disease progression or toxicity not tolerated by the patient plus follow-up or survival follow-up (max. 7 years after FPI)
Duration of the entire study	maximum 7 years after FPI (First Patient In 18.02.2021)

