In another large prospective randomized phase III study 150 patients with treatment naïve or relapsed WM in need of treatment were randomized between Ibrutinib / Rituximab (IR) Rituximab / Placebo (R). Median age was 69 years. High IPSSWM was reported in 38% of patients; 45% of patients were treatment naïve. With prolonged follow-up and a median duration of treatment of 29.5 months with IR and 15.5 months with R. Investigator-assessed major response rates ( $\geq$  PR) were 77% with IR vs 33% with R (P<0.0001); ORRs ( $\geq$  MR) were 95% vs 48% (P<0.0001), respectively. With continued IR treatment, 27% of patients achieved a VGPR compared to only 3% in the R arm. Major responses with IR stayed robust independent of MYD88/CXCR genotype. Overall time to major response was 2.0 months with IR vs 5.6 months with R (MYD88L265P/CXCR4WT: 1.8 vs 5.2; MYD88L265P/CXCR4WHIM: 2.9 vs 10.8; MYD88WT/CXCR4WT: 5.7 vs 5.7). Median investigator-assessed PFS was not reached with IR vs 20.3 months (95% CI: 11.6–31.3) with R (HR=0.219 [0.122–0.393]; P<0.0001); estimated 30mo PFS was 79% vs 41%. Among patients receiving IR, 30-months PFS estimates did not show any major differences among the different genotypes. The 30-months OS estimate was 93% with IR vs 90% with R; 31 patients on R crossed over to IR after IRC-confirmed PD. The AE profile in the IR arm was consistent with previous reports. Overall, grade  $\geq$  3 AEs occurred in 61% of patients in both arms. Incidence of grade  $\geq$  3 AEs was 53% during the first 12 months of treatment in the IR arm and increased 8% with longer follow up. SAEs occurred in 43% of IR patients vs. 33% of R patients. Similarly, incidence of SAEs was 39% during the first 12 months of treatment with IR and increased 4% with longer follow up.

These data and the approval of Ibrutinib have changed the therapeutic landscape in WM in shortest time and have fostered spread of chemotherapy-free approaches in the management of WM.

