## 8.5 Safety endpoints

Safety variables will include AEs, SAEs, laboratory parameters, ECG and vital signs. The severity of AEs will be graded using the NCI-CTCAE version 5.0 dictionary. An AE is defined as any event arising or worsening after first application / intake of study drug until 30 days after the last study drug intake. Safety variables will be summarized by means of descriptive statistics and / or frequency tables as appropriate. All AEs, drug related AEs and serious AEs will be summarized by MedDRA classification and worst CTCAE grade.

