### 9.1 Estimated study duration

Approximately 99 patients at approximately 30 study sites in Europe will be recruited. Patients will receive lbrutinib in both treatment arms until progression, non-tolerated toxicity or until the study duration has reached its maximum of 7 years after the first patient was included into the study. Patients will be followed up after end of treatment. Follow-up (5 years or until disease progression for patients who discontinue treatment due to toxicity) or survival follow-up (for patients with disease progression) will be performed until the study duration has reached its maximum of 7 years after the first patient was included into the study.

1 st patient included:	Q1 2021 (18.02.2021)		
Last patient included:	Q2 2024		
Maximal duration of study therapy/patient:	Until progression, non-tolerated toxicities or until the study		
	patient was included into the study.		
Duration of follow-up /	a) In the case that treatment is terminated because of non-		
patient:	tolerable toxicity follow up will be performed 5 years or		
	until the study duration has reached its maximum of 7		
	years after the first patient was included into the study.		
	b) In the case of progression or start of a new anti-		
	lymphoma therapy every 6 months for survival until the		
	end of the study.		
End of study:	5 years after the last included patient has finished therapy		
	or until the study duration has reached its maximum of 7		
	years after the first patient was included into the study.		

Further treatment with Ibrutinib outside this protocol, for patients who continue to benefit from the Ibrutinib treatment 7 years after first patient in, will be at the investigator's discretion

according to local practice and local commercial availability of Ibrutinib. After finishing all study relevant procedures (therapy and follow-up period), the patient will be followed in terms of routine aftercare and treated if necessary by the primary responsible hematologic-oncologic center.

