## 13.2 Monitoring, recording and reporting of adverse events

All patients will be monitored for AEs during the study. Assessments may include monitoring of the following parameters: the patient's clinical symptoms, laboratory, pathological, radiological or surgical findings, physical examination findings or other appropriate tests and procedures.

All adverse events, serious adverse events and special reporting situations, whether serious or non-serious, will be recorded from the time of first application / intake of IMPs until the patient's end of treatment visit (30 days after last intake of study drug). Additionally, all kinds of secondary malignancies have to be reported until end of study.

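### Section 14.3 compares AEs and SAEs between arms only as crude frequencies, although the AE window lasts as long as treatment and time at risk can differ by arm

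*Protocol*

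**What the plan says.** - **Test.** Section 14.3 (and the synopsis): "Group comparisons (A vs. B) of frequencies of AEs and SAEs will be performed using the chi square test" or Fisher's exact test as appropriate. Section 8.5 adds only description: "Safety variables will be summarized by means of descriptive statistics and / or frequency tables as appropriate".
- **AE window.** Section 8.5 defines an AE as "any event arising or worsening after first application / intake of study drug until 30 days after the last study drug intake". Section 13.2 agrees: AEs and SAEs "will be recorded from the time of first application / intake of IMPs until" the end-of-treatment visit, 30 days after the last intake.
- **Treatment length.** Section 9.1 has ibrutinib given "in both treatment arms until progression, non-tolerated toxicity or until the study duration has reached its maximum of 7 years" after first patient in. Under sections 11.1 and 11.3.2.1, an arm A patient who stops one drug may continue the other and still counts as on treatment. Carfilzomib ends after cycle 24.
- **Safety population.** Section 14.5.2 groups patients by treatment received. It says nothing about time at risk.

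The protocol names no person-time rate, no time-to-event analysis and no common-window comparison for AEs.

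**The concern.** Each patient's AE window closes when treatment ends, and treatment ends because of progression or intolerance. Both can differ by arm. The trial expects deeper remissions in arm A and links them to longer PFS (section 14.2), which would lengthen arm A's window. Added toxicity could shorten it. Randomisation does not protect against this, because the imbalance arises after it.

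A crude frequency mixes the risk of an event with the time over which events are counted. If arm A stays on treatment longer, it can look more toxic than it is. If arm A stops early because of toxicity, real excess harm can be hidden. The combination is not approved in this indication (section 13.1), so its safety profile relative to ibrutinib alone is something readers will want from this trial.

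**Working it through.** The protocol states no safety figure to reproduce. Section 14.3 sets no level for the AE tests, so a two-sided 5% chi-square test is assumed.

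**1. Equal constant hazard, unequal treatment time**

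Assumptions: AE hazard λ = 0.03 per month in both arms; 50 patients per arm; exponential treatment time with median m, so μ = ln 2 / m; cap at 60 months; one further month for the 30-day tail.

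The cap lies within the range the protocol allows. The study ends 7 years after 18.02.2021, which gives 7.0 years for the first patient and 3.6 to 3.9 years for one entering in Q2 2024.

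P(AE) = 1 − e^(−λ) × [ μ/(μ+λ) × (1 − e^(−60(μ+λ))) + e^(−60(μ+λ)) ]

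- m = 29.5: μ = 0.0235, bracket = 0.462, P = 1 − 0.970 × 0.462 = 55%.
- m = 15.5: μ = 0.0447, bracket = 0.603, P = 1 − 0.970 × 0.603 = 41%.
- m = 40: bracket = 0.403, P = 61%.
- m = 30: bracket = 0.458, P = 56%.

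Summing the two binomial distributions over the rejection region gives:

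| Median treatment (months) | Crude AE % | Significant although hazards are equal |
|---|---|---|
| 29.5 vs 15.5 | 55 vs 41 | about 30% |
| 40 vs 30 | 61 vs 56 | about 9% |
| equal | equal | about 5% |

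The gap in the first row is the "median duration of treatment of 29.5 months with IR and 15.5 months with R" that section 7.4 reports for ibrutinib/rituximab against placebo/rituximab.

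**2. Front-loaded events**

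A hazard of 3% per month gives 1 − e^(−0.36) = 30% by month 12. Section 7.4 reports much faster early accrual on ibrutinib/rituximab: grade ≥3 AEs 53% in the first 12 months, rising by 8 points to 61%; SAEs 39%, rising by 4 points to 43%. Suppose one arm stops at about 12 months and the other continues. With 50 per arm:

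- 53% vs 61%: rejection about 14%.
- 39% vs 43%: rejection about 7%.

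**3. Masking**

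Assume true rates of 0.30 (A) and 0.15 (B) per year, 47 per arm, and P = 1 − e^(−rate × (years + 30/365.25)).

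- Exposure 2 years (A) vs 4 years (B): 46.5% vs 45.8%. The chance of detecting an excess in A is 2.8%.
- Exposure 3 years in both arms: 60% vs 37%. The chance is 62%.

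**4. Remedies that do not remove the problem**

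Take the equal-hazard scenario with 29.5 vs 15.5 months and look only at the first 24 cycles (24 × 28 = 672 days, about 22 months).

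- Crude percentage in 24 cycles plus 30 days: 41% vs 34%, rejection about 10%.
- Treatment stop as a competing event: 39% vs 32%, rejection about 10%.

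Both still depend on how long patients stay on treatment. A single patient-year rate has the opposite weakness. When events come early and carfilzomib ends after cycle 24, late low-risk time dilutes carfilzomib toxicity in an arm that stays on longer.

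**The case against.** **The large figure comes from an unsuitable comparison.** In the cited trial the control arm received no ibrutinib. Here both arms take it continuously. A reader might infer from 29.5 vs 15.5 months that a gap of this size, and so a false-difference rate near 30%, is to be expected. The documents do not support that, because they predict no exposure by arm. The milder case gives about 9%, and the front-loaded figures themselves assume one arm stopping at about 12 months. This objection stands, and it limits the size of the point.

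**The tests are exploratory.** A reader might infer that the benefit-risk decision rests on the AE tests. The protocol does not say so. Section 14.2 ties the justification to the rise in CR/VGPR from 16% to 35%, section 14.3 treats all secondary endpoints as exploratory, and no decision rule attaches to the AE tests. The DSMC reviews safety early, by cycles completed (section 15). This stands too, but an exploratory label does not make a comparison confounded by exposure easier to read.

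**There are partial safeguards.** Time to treatment failure counts stopping for toxicity (section 14.1.2). Related SAEs are reported whenever they occur (section 13.7), and secondary malignancies until end of study (section 13.2). These make early toxic stopping visible, but they do not correct the AE comparison.

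**An SAP could add exposure-adjusted summaries.** It could, and the protocol does not exclude them. But the protocol names the between-arm method itself, so the point concerns a stated method rather than an omitted detail.

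**The on-treatment percentage is legitimate.** It describes the total AE burden of the assigned regimen, and should be kept for that purpose.

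**Conclusion.** The point holds in a limited form. Section 14.3 names only a crude frequency test for a quantity whose observation time is set by efficacy and tolerability, so the result can mislead in either direction.

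The size cannot be fixed from the documents. Against a nominal 5%, false differences run from about 7% to 14% for front-loaded events and from about 9% to 30% under an equal constant hazard. The 30% is an extreme borrowed from another treatment comparison. All these figures rest on assumed hazards and durations. If exposure turns out similar in the two arms, the problem largely disappears. The primary analysis and the sample size are not affected.

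**What to change.** In section 14.3:

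1. Keep the crude percentages and the chi-square or Fisher tests, labelled as a description of on-treatment AE burden.
2. Report treatment exposure by arm.
3. Make the between-arm comparison on time to first AE and first SAE, with patients censored at the end of their AE window and death as a competing event.
4. Report exposure-adjusted incidence rates beside it (rate ratio with 95% CI), split by period, for example cycles 1–12, 13–24 and 25 onwards. The split is needed because the hazard is not constant and carfilzomib ends after cycle 24.
5. Do not use treatment stop as a competing event, or a crude fixed-window percentage, as the exposure correction.

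The censored analysis assumes that stopping treatment carries no information about later AE risk. That may fail when patients stop for toxicity, so time to treatment failure should be read beside it.

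The cost is a little programming. AE start and stop dates (section 13.4.5), carfilzomib administration (section 11.3.1.1) and ibrutinib intake (section 11.5.6) are already recorded. Sample size and trial conduct do not change.
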